### **6.2.3     Rescue medication**

Second generation H1-antihistamines that are eliminated primarily via renal excretion (e.g. cetirizine, levocetirizine or bilastine) are allowed as rescue medication (at a locally approved licensed posology), used on an as needed basis for subjects with flare-ups of unbearable symptoms of their disease throughout the study. The selection of the H1-antihistamines rescue medication should be made only once for an individual subject and documented in the source document. For each individual subject, the H1-antihistamine rescue medication used must differ from the H1-antihistamine used for background medication (if used). For detailed information on the rescue medication, refer to the corresponding SmPC. The rescue medication should be changed only if deemed necessary by the investigator.

## **6.3     Subject numbering, treatment assignment, randomization**

### **6.3.1    Subject numbering**

Each subject is identified in the study by a Subject Number (Subject No.), that is assigned when the patient is first enrolled and is retained as the primary identifier for the subject throughout his/her entire participation in the trial. The Subject No. consists of the Center Number (Center No.) (as assigned by Novartis/sponsor to the investigative site) with a sequential subject number suffixed to it, so that each subject is numbered uniquely across the entire database. Upon signing the informed consent form, the patient is assigned to the next sequential Subject No. available. Each subject number in this extension study will be linked to the respective study number in the core study via Prior study participation form.

### **6.3.2    Treatment assignment, randomization**

After enrollment, subjects will be assigned to the treatment period or the observational period based on their UAS7 score (see [Section 5](#)).

## **6.4     Treatment blinding**

Treatment will be open to subjects, investigator staff, persons performing the assessments, and the CTT.

## **6.5     Dose escalation and dose modification**

Investigational or other study treatment dose adjustments and/or interruptions are not permitted.

## **6.6     Additional treatment guidance**

### **6.6.1    Treatment compliance**

The investigator must promote compliance by instructing the subject to take the study treatment exactly as prescribed and by stating that compliance is necessary for the subject's safety and the validity of the study. The patient must take two capsules of LOU064 50 mg in the morning and two capsules of LOU064 50 mg in the evening with a dosing interval of approximately

12 hours. The subject must also be instructed to contact the investigator if he/she is unable for any reason to take the study treatment as prescribed. Compliance with study treatment will be recorded by the subject in the eDiary. In addition, compliance will be assessed by the investigator and/or study personnel at each visit using capsules counts and information provided by the subject and captured in the source document at each visit. All study treatment dispensed and returned must be recorded in the Drug Accountability Log.

### **6.6.2 Emergency breaking of assigned treatment code**

Not applicable.

## **6.7 Preparation and dispensation**

Each study site will be supplied with study drug in packaging as described under investigational and control drugs [Section 6.1.1](#).

An IRT system would be used in the study for medication management purposes.

Investigator staff will identify the study medication kits to dispense to the subject by contacting the IRT and obtaining the medication number(s). The study medication has a 2-part label (base plus tear-off label), immediately before dispensing the medication kit to the subject, site personnel will detach the outer part of the label from the packaging and affix it to the source document.

At each dispensation visit, study personnel delegated for this activity would contact IRT and provide the patient with the assigned bottles to accommodate patient needs till the next dispensation visit. The number of bottles dispensed would vary depending on the duration between visits.

As per [Section 4.6](#), during a Public Health emergency as declared by Local or Regional authorities, i.e., pandemic, epidemic or natural disaster, that limits or prevents on-site study visits, delivery of IMP directly to a participant's home may be permitted (if allowed by Local or Regional Health Authorities and Ethics Committees as appropriate) in the event the Investigator has decided that an on-site visit by the participant is no longer appropriate or possible and that it is in the interest of the participant's health to administer the study treatment even without performing an on-site visit. The dispatch of IMP from the site to the participant's home remains under the accountability of the Investigator. Each shipment/provisioning will be for a maximum of one-month supply. In this case, regular phone calls or virtual contacts (every 4 weeks or more frequently if needed) will occur between the site and the participant for instructional purposes, safety monitoring, drug accountability, investigation of any adverse events, ensuring participants continue to benefit from treatment, and discussion of the participant's health status until the participants can resume visits at the study site.

### **6.7.1 Handling of study treatment and additional treatment**

#### **6.7.1.1 Handling of study treatment**

Study treatment must be received by a designated person at the study site, handled and stored safely and properly and kept in a secured location to which only the investigator and designated site personnel have access. Upon receipt, all study treatment must be stored according to the

instructions specified on the labels and in the Investigator's Brochure. Clinical supplies are to be dispensed only in accordance with the protocol. Technical complaints are to be reported to the respective Novartis CPO Quality Assurance.

Medication labels will be in the local language and comply with the legal requirements of each country. They will include storage conditions for the study treatment but no information about the subject except for the medication number.

The investigator must maintain an accurate record of the shipment and dispensing of study treatment in a drug accountability log. Monitoring of drug accountability will be performed by monitors during site visits or remotely and at the completion of the trial. Subjects will be asked to return all unused study treatment and packaging at the end of the study or at the time of discontinuation of study treatment.

At the conclusion of the study, and as appropriate during the course of the study, the investigator will return all unused study treatment, packaging, drug labels, and a copy of the completed drug accountability log to the Novartis monitor or to the Novartis address provided in the investigator folder at each site.

[REDACTED]

[REDACTED]

[REDACTED]

#### **6.7.2 Instruction for prescribing and taking study treatment**

Subjects should take 2 capsules of LOU064 50 mg twice daily with a 12 hour interval in the morning and in the evening at approximately the same time each day. Subjects should take LOU064 without regard to food. Each dose may be taken with a glass of water.

[REDACTED]

Subjects should be instructed to swallow whole capsules and not to chew or open them.

If vomiting occurs during the course of treatment, subjects should not take the study treatment again before the next scheduled dose.

Subjects should be instructed not to make up missed doses. A missed dose is defined as a case when the full dose is not taken within 4 hours after the approximate time of the usually morning/evening dosing. This dose should be omitted and the subject should continue treatment with the next scheduled dose.

Study medication intake will be recorded in the patient's eDiary. Subjects will be instructed to complete eDiary entries after they took their study medication throughout the treatment period.

[REDACTED]

All kits of study treatment assigned by the IRT will be recorded in the IRT system.

## **7 Informed consent procedures**

Eligible subjects may only be included in the study after providing (witnessed, where required by law or regulation), IRB/IEC-approved informed consent.

[REDACTED]

If applicable, in cases where the subject's representative(s) gives consent (if allowed according to local requirements), the subject must be informed about the study to the extent possible given his/her understanding. If the subject is capable of doing so, he/she must indicate agreement by personally signing and dating the written informed consent document.

Informed consent must be obtained before conducting any study-specific procedures (e.g. all of the procedures described in the protocol). The process of obtaining informed consent must be documented in the subject source documents.

Novartis will provide to investigators in a separate document a proposed informed consent form that complies with the ICH GCP guidelines and regulatory requirements and is considered appropriate for this study. Any changes to the proposed consent form suggested by the investigator must be agreed by Novartis before submission to the IRB/IEC.

Information about common side effects already known about the investigational drug can be found in the Investigator's Brochure (IB). This information will be included in the subject informed consent and should be discussed with the subject during the study as needed. Any new information regarding the safety profile of the investigational drug that is identified between IB updates will be communicated as appropriate, for example, via an investigator notification or an aggregate safety finding. New information might require an update to the informed consent and then must be discussed with the subject.

Women of child bearing potential must be informed that taking the study treatment may involve unknown risks to the fetus if pregnancy were to occur during the study and agree that in order to participate in the study they must adhere to the contraception requirements.

A copy of the approved version of all consent forms must be provided to Novartis/sponsor after IRB/IEC approval.

The study includes the option for the participant to have certain study procedures performed off-site by an off-site healthcare professional instead of at the study site, for which a separate signature is required if the participant agrees. It is required as part of this protocol that the Investigator presents this option to the participant, as permitted by national and local governing regulations. The process for obtaining consent should be exactly the same as described above for the main informed consent.

As per [Section 4.6](#), during a Public Health emergency as declared by Local or Regional authorities i.e. pandemic, epidemic or natural disaster, that may challenge the ability to obtain a standard written informed consent due to limits that prevent an on-site visit, Investigator may conduct the informed consent discussion remotely (e.g. telephone, videoconference) if allowable by a local Health Authority.

Guidance issued by local regulatory bodies on this aspect prevail and must be implemented and appropriately documented (e.g. the presence of an impartial witness, sign/dating separate ICFs by trial participant and person obtaining informed consent, etc.).

## **8 Visit schedule and assessments**

The assessment schedule lists all of the assessments and indicates with an "X" or "S", the visits when they are performed. All data obtained from these assessments must be supported in the subject's source documentation.

Subjects should be seen/contacted for all visits/assessments as outlined in the assessment schedule or as close to the designated day/time as possible. Missed or rescheduled visits should not lead to automatic discontinuation.

As per [Section 4.6](#), during a Public Health emergency as declared by Local or Regional authorities, i.e., pandemic, epidemic or natural disaster that limits or prevents on-site study visits, alternative methods of providing continuing care may be implemented by the investigator as the situation dictates. If allowed by local Health Authority and depending on operational capabilities, phone calls, virtual contacts (e.g., tele consult) or visits by site staff/home nursing staff to the participant's home can replace on-site study visits for the duration of the disruption until it is safe for the participant to visit the site again.

**Table 8-1 Assessment Schedule, Treatment period and Follow-up period**

Period	Open Label Treatment										Treatment free follow-up			Unscheduled visit
Visit	Screening								EoTV 				Study Completion Visit 	
Days	1	29	57	85	113	141	197	281	365 (or early termination)	393 	421  	449  	393-477	NA
Weeks	1	4	8	12	16	20	28	40	52	56	60	64	56-68	NA
Informed consent	X													
Prior study participation	X													
Inclusion / Exclusion criteria	X													
Demography	X													
Physical Examination 	S 	S	S	S	S	S	S	S	S	S			S	S
Vital Signs	X 	X	X	X	X	X	X	X	X	X			X	X
Body Weight	X 						X		X				X	X
Electrocardiogram (ECG)	X 	X	X	X		X	X	X	X				X	X
Concomitant medications	X 	X	X	X	X	X	X	X	X	X	X	X	X	X
Adverse Events	X 	X	X	X	X	X	X	X	X	X	X	X	X	X
Drug dispensation	X	X	X	X	X	X	X	X						X
IRT transaction	X	X	X	X	X	X	X	X	X					X

Period	Open Label Treatment									Treatment free follow-up			Unscheduled visit	
Visit	Screening								EoTV 				Study Completion Visit 	
Days	1	29	57	85	113	141	197	281	365 (or early termination)	393 	421  ☎	449  ☎	393-477	NA
Weeks	1	4	8	12	16	20	28	40	52	56	60	64	56-68	NA
Subjects' eDiary review  - UPDD (incl. UAS)	S 	S	S	S	S	S	S	S	S	S	S	S	S	S
Study drug compliance Assessment		S	S	S	S	S	S	S	S					S
Urinalysis	X 	X	X	X	X	X	X	X	X	X			X	X
Clinical Chemistry	X 	X	X	X	X	X	X	X	X	X			X	X
Hematology	X 	X	X	X	X	X	X	X	X	X			X	X
Coagulation Panel	X 						X		X				X	X
Total IgE				X		X		X					X	X
Pregnancy Test (serum) 	X													
Pregnancy test (urine) 		S	S	S	S	S	S	S	S	S			S	S

Period	Open Label Treatment									Treatment free follow-up				Unscheduled visit
Visit	Screening								EoTV 				Study Completion Visit 	
Days	1	29	57	85	113	141	197	281	365 (or early termination)	393 	421  ☎	449  ☎	393-477	NA
Weeks	1	4	8	12	16	20	28	40	52	56	60	64	56-68	NA
Check eligibility for entering extended Follow-up (up to 16 weeks)									S					
Disposition (end of treatment and study disposition)	X													

X: recorded in the eCRF; S: recorded in the source documents only

 Detailed description of physical exam in [Table 8-9](#). Complete physical exam: day 1 of the treatment period. Short physical exam: all other visits.

 UPDD: Urticaria Patient Daily Diary; UAS: Urticaria Activity Score;

 Only performed in women of childbearing potential

 Only performed in women of childbearing potential. In addition to tests during study visits, urine pregnancy tests can be performed at home at Week 24, 32, 36, 44, and 48. Sites must contact subjects to obtain test results. Any positive or undetermined test result must be confirmed by a serum pregnancy test done by central lab.

 Only assess if day 1 is more than 1 week after roll-over date from core study (Week 12 or Week 16)

 Only assess if subjects rollover at Week 16 or if subjects rollover at Week 12 and day 1 of treatment period is more than 1 week after Week 12 of core study

 EoTV (End-of-Treatment Visit) is after completion of the treatment period (Week 52 Visit), or directly after early discontinuation of study treatment (see [Section 9.1](#))

 Only for subjects eligible for extended follow-up

 Phone call visits: after Week 56, all eligible subjects in extended follow-up should be contacted every 4 weeks by phone until Study Completion visit which is a site visit

 SCV (Study Completion Visit) is 4-16 weeks after EoTV:

- all subjects should be followed-up for a minimum of 4 weeks after EoTV
- the extended follow-up of eligible subjects (completion of treatment period and a UAS7≤6 at Week 52) should be stopped after relapse of CSU, initiation of a prohibited therapy (see [Section 6.2.2](#)), decision of the subject or the investigator to stop the follow-up, rolling-over into a post-trial access program (if available), or reaching the maximum follow-up time (16 weeks, Week 68 Visit)

**Table 8-2 Assessment Schedule, Observational period**

Visit	Screening			EoOP 	Unscheduled visit
Days	1	29 	57 	8-85	NA
Weeks	1	4	8	1-12	NA
Informed consent	X				
Prior study participation	X				
Inclusion / Exclusion criteria	X				
Demography	X				
Short Physical Examination	S			S	S
Adverse Events	X 	X	X	X	X
Concomitant medications	X 	X	X	X	X
Subjects' eDiary review  : - UPDD (incl. UAS)	S 	S	S	S	S
Clinical Chemistry		X	X	X	X
Hematology		X	X	X	X
Total IgE				X	X
Study disposition			X		

X: recorded in the eCRF; S: recorded in the source documents only

 UPDD: Urticaria Patient Daily Diary; UAS: Urticaria Activity Score; [REDACTED]

 Only assess if day 1 of observational period is more than 1 week after Week 16 of core study

 If CSU relapse is detected at the visit: please directly perform an EoOP visit instead of the preplanned day 29 or day 57 visit

 EoOP: End of Observational Period can be directly after a CSU relapse (defined as UAS7≥16) was detected (either during a scheduled or an unscheduled visit); in case, EoOP and day 1 of the treatment period are at the same day, assessments only need to be done once.  
[REDACTED]

## **8.1 Screening**

At day 1 of the treatment period and at day 1 of the observational period (if applicable), all inclusion and exclusion criteria will be checked. For all laboratory assessments, the results from the last visit before Day 1 of the treatment period (either the last available value from CLOU064A2201 or most recent value taken during observational period) will be used.

Eligibility for this study will be assessed at Week 12 and Week 16 of the preceding core study CLOU064A2201. Subjects who are not eligible for enrollment into this extension study at Week 12 for any reason will not be assigned to a subject number for this extension study but will enter the follow-up period of CLOU064A2201. Re-screening of subjects who are not eligible at Week 16 is not permitted.

### **8.1.1 Information to be collected on screening failures**

Patients who sign an informed consent but fail to be started on treatment for any reason other than never relapsing during the observational period will be considered a screen failure. The reason for not being started on treatment will be entered on the screening phase disposition page. The demographic information, informed consent, and Inclusion/Exclusion pages must also be completed for screen failure patients. No other data will be entered into the clinical database for patients who are screen failures, unless the patient experienced a serious adverse event during the screening phase (see SAE Section for reporting details).

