## **12 Data analysis and statistical methods**

### **12.1 Analysis sets**

The **Safety Analysis Set (SAF)** includes all subjects who received at least one dose of study treatment during the treatment period of this extension study.

For the observational period, the observational Full Analysis Set (**oFAS**) includes all subjects who enrolled in the observational period.

All enrolled subjects includes all subjects who enrolled in this extension study.

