#### **12.4.2 Statistical model, hypothesis, and method of analysis**

No hypothesis testing is planned for the primary objective.

Summary statistics for continuous variables will include N, mean, standard deviation, minimum, lower quartile, median, upper quartile, maximum.

Summary statistics for discrete variables will be presented in contingency tables and will include absolute and relative frequencies.

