## **12.8 Sample size calculation**

### **12.8.1 Primary endpoint(s)**

It is expected that approximately 250 subjects from CLOU064A2201 study will enroll in this extension study.

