### **2.3 Patient disposition, demographics and other baseline characteristics**

#### **2.3.1 Patient disposition**

The number of screened and screen failures subjects will also be shown for all enrolled subjects. The reason for screen failure will be summarized.

The number of subjects in each analysis set will be presented by observational period based on oFAS and treatment period based on Safety set. The reason for excluded from any analysis set will be listed.

The number and percentage of patients enrolled in observational period, complete observation period or early discontinued from study during observational period will be presented based on oFAS. Similarly, the number and percentage of patients enrolled in treatment period, complete the treatment period or early discontinued from treatment/study will be presented based on SAF.

The number and percentage of patients who has experienced protocol deviations (PD) will be tabulated by deviation category for all patients.

Listing will be provided for all subjects enrolled.

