## **2.7 Safety analyses**

### **2.7.1 Adverse event during observational period**

Adverse event and serious adverse event during observational period will be summarized by primary system organ class and preferred term for OFAS.

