##### Impute AE start date:

Before imputing AE start date, find the AE start reference date as below

- If the (imputed) AE end date is complete and the (imputed) AE end date < treatment start date then AE start reference date = min(informed consent date, earliest visit date).
- Else AE start reference date = treatment start date

1. If the AE start date 'year' value is missing, the date uncertainty is too high to impute a rational date. Therefore, if the AE year value is missing, the imputed AE start date is set to NULL.
2. If the AE start date 'year' value is less than the treatment start date year value, the AE started before treatment. Therefore:

- a. If AE 'month' is missing, the imputed AE start date is set to the mid-year point (01JulYYYY).
- b. Else if AE 'month' is not missing, the imputed AE start date is set to the mid-month point (15MONYYYY).

3. If the AE start date year value is greater than the treatment start date year value, the AE started after treatment. Therefore:

- a. If the AE month is missing, the imputed AE start date is set to the year start point (01JanYYYY).
- b. Else if the AE month is not missing, the imputed AE start date is set to the later of (month start point (01MONYYYY), AE start reference date + 1 day).

4. If the AE start date year value is equal to the treatment start date year value:

- a. And the AE month is missing the imputed AE start date is set to the AE reference start date + 1 day.
- b. Else if the AE month is less than the treatment start month, the imputed AE start date is set to the mid-month point (15MONYYYY).
- c. Else if the AE month is equal to the treatment start date month or greater than the treatment start date month, the imputed AE start date is set to the later of (month start point (01MONYYYY), AE start reference date + 1 day).

If complete (imputed) AE end date is available and the imputed AE start date is greater than the (imputed) AE end date, then imputed AE start date should be set to the (imputed) AE end date.

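### Protocol 8.1.1 bars entry of non-serious AEs for subjects who leave the observational period untreated, contradicting Table 8-2 and the oFAS AE summary; separately, the SAP does not say how AEs with no start year are classified

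*Protocol*

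**What the plan says.** **Screen failures.** Protocol 8.1.1 applies the label to subjects who consent but "fail to be started on treatment for any reason other than never relapsing during the observational period". For them the disposition, demography, consent and eligibility pages are completed. Beyond that, "No other data will be entered into the clinical database for patients who are screen failures", with an exception for a serious event in the screening phase.

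**Observational period.** Table 8-2 marks adverse events and concomitant medications for the eCRF at Day 1 (conditionally), Days 29 and 57, the end-of-period visit and unscheduled visits. Chemistry and hematology are marked at all of these except Day 1. No exception is made for subjects later called screen failures. Protocol 12.1 defines oFAS as the set that "includes all subjects who enrolled in the observational period". SAP 2.7.1 states: "Adverse event and serious adverse event during observational period will be summarized by primary system organ class and preferred term", for oFAS; Protocol 12.5.2 says the same and adds a listing of all AEs for all enrolled subjects. SAP 2.3.1 provides that subjects who "early discontinued from study during observational period will be presented based on oFAS".

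**AE start dates.** SAP 5.1.2 says that "if the AE year value is missing, the imputed AE start date is set to NULL". SAP 2.5.1.1 defines a treatment-emergent AE by onset, or by worsening, on or after first dose.

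**The concern.** A subject who enters the observational period and then withdraws, stops because of an AE, or relapses but fails a criterion on Day 1 of treatment is a screen failure under 8.1.1. The same subject is an oFAS member with AEs to be summarised under 12.1 and 12.5.2, and an early discontinuation under SAP 2.3.1. The subject counts in the denominator whichever instruction the site follows; whether the AEs reach the numerator depends on the site.

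Such a loss would be informative. Some of these subjects leave because of an AE or an abnormal laboratory result, and their non-serious events are the ones at risk of not being entered. The table would look cleaner than the experience it describes, and completeness could differ between sites.

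The second issue is smaller. An AE with no usable start date cannot show onset on or after first dose, and the SAP does not say what to do with it. This touches the primary safety tables, though probably for very few events.

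**Working it through.** The plan offers no figure to reproduce. "No hypothesis testing is planned for the primary objective", and the only sample-size statement is an expectation that "approximately 250 subjects from CLOU064A2201 study will enroll in this extension study" (250 of the 308 expected in the core study, 81%). The check is a comparison of passages.

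**1. Does 8.1.1 reach the observational period?** Yes, read literally. An exception for never-relapsers is needed only if other subjects in that period fall under the rule. Protocol 10.1.3 also gives, as its example of a screen failure, someone screened but not treated.

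**2. Can such subjects arise?** Yes. Protocol 8.1 has all criteria checked again at Day 1 of treatment. Exclusion criteria 16, 21 and 22 use the latest laboratory values, including those from the observational period, and criterion 6a uses a Day 1 ECG. Section 3 says relapsers may enter treatment, so entry is not automatic.

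**3. What does each passage require for one such subject?**

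| Source | Consequence |
|---|---|
| Protocol 8.1.1 | screen failure; no non-serious AEs, labs or medications entered |
| Protocol Table 8-2 | AEs, labs and medications recorded in the eCRF |
| Protocol 12.1, SAP 2.2 | member of oFAS |
| SAP Table 5-1 | oFAS exclusions are consent and severe GCP failures; screen failure is not listed |
| Protocol 12.5.2, SAP 2.7.1 | AEs summarised on oFAS |
| SAP 2.3.1 | early discontinuation within oFAS |

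Row 1 conflicts with row 2 directly, and with the last four through the denominator.

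**4. Direction and form of the error.** Let n be the size of oFAS and m the number of untreated leavers other than never-relapsers. Let q be the proportion of leavers with at least one non-serious AE, and c the proportion of those who still have one in the database. Then true minus reported incidence = (m/n) × q × (1 − c). This is never negative, so the error can only understate. None of m, n, q or c is in the documents.

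**5. Illustration on assumed inputs only.** Take n = 60, the same AE rate p in leavers and stayers, and nothing entered for leavers (c = 0). Reported incidence = p × (n − m)/n.

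| m (share) | p = 20% | p = 40% |
|---|---|---|
| 3 (5%) | 19% | 38% |
| 6 (10%) | 18% | 36% |
| 12 (20%) | 16% | 32% |

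Under these assumptions the relative understatement equals the share of leavers. A higher AE rate in leavers would enlarge it; AEs entered before exit would shrink it.

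**6. NULL start dates.** A missing date fails a plain on-or-after comparison (checked: it returns false), so the onset limb is not met by default. The worsening limb makes no reference to the start date. No passage classifies the event. By contrast, SAP 5.1.3 gives a medication with missing start year a definite date, the day before treatment start. SAP 5.1.2 itself compares the AE end date with treatment start to choose a reference date, but does not use the result when the year is missing. If one subject's only event for a term is left out, incidence falls by 1/250 = 0.4 points at N = 250, or 1/200 = 0.5 points at an assumed N = 200. For a rare term, 1/250 (exact 95% CI 0.01% to 2.21%) would be shown as 0/250 (0% to 1.46%).

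**The case against.** The strongest reply is that 8.1.1 was meant for screening alone. It speaks of a screening phase and a screening disposition page, Table 8-2 labels only Day 1 as screening and has its own study disposition row, and the glossary defines a screen failure as someone who did not meet a criterion. On that reading an eligible subject who later withdraws is simply an early discontinuation, as SAP 2.3.1 has it. This is probably the sensible intention, but the never-relapser exception in 8.1.1 does not fit it, and a site has to work from the wording.

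A reader might infer that all non-serious AEs of these subjects are lost. The documents do not support that. Events entered at Day 29 or 57 precede any later label, nothing tells sites to delete them, and Protocol 11.2 has central laboratory results sent to the sponsor electronically. Incomplete is the accurate word.

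A reader might also take the oFAS table as the trial's only treatment-free safety information. It is not: every subject who stops LOU064 is to have at least 4 weeks of treatment-free follow-up, with AEs recorded (Section 3, Table 8-1). Nor is oFAS a planned comparator in this single-arm, descriptive study.

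Finally, a reader might conclude that an AE with a NULL start can never be treatment-emergent. No passage says so. The worsening limb stays open, the event remains in the listings (SAP 2.5.1.1, Protocol 12.5.2), and the case should be rare because AEs are sought at every visit and conditions present at consent go to medical history.

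**Conclusion.** The contradiction is real and should be corrected. Protocol 8.1.1 cannot be followed together with Table 8-2, the oFAS definition and AE summary, and SAP 2.3.1. Where 8.1.1 is followed, observational-period incidence of non-serious AEs is understated. The direction is certain; the amount cannot be sized from the documents, and the illustration above is not an estimate. The effect is confined to the observational-period outputs: these subjects received no study treatment, so they are not in the safety set and the primary analysis is unaffected.

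The NULL-start gap is secondary and minor. It does concern the primary AE tables. If the gap is left to default programming, an affected event that is not recorded as worsening goes uncounted, at 0.4 points per affected subject if the safety set numbers 250, and slightly more if it is smaller. The number of such events is not given and is likely to be very small.

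**What to change.** 1. **Protocol 8.1.1.** Limit the no-data rule to subjects who enter neither the observational nor the treatment period. Class subjects who entered the observational period but were not treated, other than never-relapsers, as discontinued during that period, with AEs, laboratory data and medications kept as Table 8-2 requires. Align the eCRF guidance.

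2. **Data already affected.** About 227 subjects had rolled over by Amendment 2, and the last SAP update is dated just before the final analysis, so rewording alone will not recover unentered events. Retrieve them from source, where Section 8 requires the assessments to be supported. Failing that, report beside the observational AE table how many oFAS subjects have no AE data.

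3. **SAP 5.1.2.** Add that an AE with missing start year counts as treatment-emergent unless a known end date precedes first dose. This is a reasonable default: AEs are post-consent by definition, and for subjects entering treatment directly, consent is scheduled on Day 1.

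Cost: a protocol clarification, eCRF guidance, one SAP sentence and some retrospective data entry. No new procedures. AE counts may rise slightly.
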